- (2) Positron Emission Tomography Methods: Data Acquisition: CUD subjects will participate in two [18F]FPEB scans, while controls will participate in one. Given we and others recently showed a diurnal variation in mGluR5 availability, all mGluR5 scan collection will be at the same time of day. [18F]FPEB will be synthesized in the Radiochemistry Laboratory at the Yale PET Center. 79 The HRRT, or a PET/CT, will be used to image subjects. [18F]FPEB will be administered as either a single bolus lasting up to one minute or bolus plus constant infusion lasting up to 2 hours. In either case, [18F]FPEB will be prepared in a single syringe and administered via software-controlled pump to achieve the desired radiotracer administration schedule not to exceed 5mCi. Syringe and lines will be assayed after scanning to correct for residual activity. Subjects are infused outside the scanner for the first 0-90 minutes during the pre-equilibrium period. Then, they will be scanned for 30 minutes in list-mode during the time the radiotracer reaches steady levels in the brain (90-120 minutes). At the beginning or end of each scan, a transmission scan, or low dose CT, will be obtained and used for attenuation correction. The emission list-mode data will then be binned into 5-min frames, and images will be reconstructed, correcting for attenuation, scatter, randoms, deadtime, and motion (using data from the Polaris Vicra using the MOLAR algorithm^89). Pulse and blood pressure will be obtained before, during, and after scanning. Input Function Measurement: Venous concentrations of [18F]FPEB reach equilibrium by 60 minutes post injection. Therefore,  $V_T$  can be determined from the ratio of activity in tissue to that in venous blood samples. Blood samples will be acquired manually before and during the equilibrium period (90-120 minutes). If the individuals from CUD group are also participating in HIC# 2000032181 and already has an has an arterial line placed, blood may be drawn through the arterial line if intravenous access is unobtainable. Radioactivity concentration in whole blood and plasma will be measured using a gamma counter (Wizard 1480; Perkin-Elmer, Waltham, MA, USA). Up to 6 tablespoons of blood will be drawn per PET scan. Highperformance liquid chromatography (HPLC) will be used to establish unmetabolized parent compound levels. The input function is calculated as the product of the interpolated parent fraction and the plasma concentration values. PET Image Analysis: To compute regional values, a summed PET image will be registered to each subject's T1- weighted MR image

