## Positron Emission Tomography (PET) Sessions

PET procedures will be conducted at the Yale University PET Center. Female subjects of child bearing potential will be given a urine pregnancy test prior to the initiation of any imaging procedures. If the test is positive, the scan session will be canceled. HCs will complete a single PET scan session. CUD subjects will complete up to 2 PET scan sessions, one at baseline and one following cannabis abstinence.

PET scans are acquired as subjects lie supine on the scanner bed. Vital signs (blood pressure, pulse, respiration) will be obtained before and after radiotracer administration. A venous catheter will be used for IV administration of the radiotracer and for venous blood sampling. PET scans will be acquired using bolus plus constant infusion administration of ≤5 mCi of [¹8F]FPEB. Subjects are infused outside the scanner for the first 0-90 minutes during the pre-equilibrium period. Then, they will be scanned for 30 minutes in list-mode during the time the radiotracer reaches steady levels in the brain (90-120 minutes).

In the event that scans are not able to be completed as scheduled, subjects may be asked to return on another day to complete the scan. If a scan is canceled following radiotracer injection, subjects may receive an additional injection during their return visit, for a maximum of up to 2 injections (HC) or 3 injections (CUD).

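### The synopsis permits a single-bolus [18F]FPEB scan, Section 6.1.1 does not, and the only V_T method given is an equilibrium ratio that is generally not V_T after a bolus

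*Combined protocol and SAP*

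**What the plan says.** **Tracer administration.** The synopsis (Receptor Quantification Methods, item 2) says [18F]FPEB "will be administered as either a single bolus lasting up to one minute or bolus plus constant infusion lasting up to 2 hours". The sentence after it covers syringe preparation and pump delivery for both options, so the bolus option looks deliberate. Section 6.1.1, under PET Sessions, gives one mode: "PET scans will be acquired using bolus plus constant infusion administration of" up to 5 mCi. Section 6.1.2 limits activity and number of scans but does not mention the mode.

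**Acquisition.** In the synopsis the infusion runs before the subject enters the scanner, and no emission data are collected until 90 minutes. Of the imaging itself it says "they will be scanned for 30 minutes in list-mode during the time the radiotracer reaches steady levels in the brain (90-120 minutes"). Section 6.1.1 repeats this schedule.

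**Estimator.** Venous concentrations are said to "reach equilibrium by 60 minutes post injection", and on that basis V_T "can be determined from the ratio of activity in tissue to that in venous blood samples". Sampling is described as "Blood samples will be acquired manually before and during the equilibrium period (90-120 minutes"). A metabolite-corrected input function is described, but no compartmental or graphical model is named.

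**Blood source.** For CUD subjects also enrolled in the companion study who already have an arterial line, "blood may be drawn through the arterial line if intravenous access is unobtainable".

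**Use of V_T.** Gray-matter-masked V_T is the primary outcome measure (synopsis, Gray Matter Masking). Section 9.2 averages V_T over six regions and uses that mean in every PET analysis.

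**The concern.** A tissue-to-plasma ratio equals V_T when both concentrations are steady. An infusion is designed to bring that about; a single bolus is not, because plasma is still falling at 90-120 minutes and tissue lags behind it. The ratio then mixes receptor binding with the subject's tracer clearance.

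The plan therefore permits a mode for which its only stated estimator does not measure the primary outcome, and its two descriptions of tracer administration disagree. Nothing requires the same mode in CUD subjects and controls, or at Day 0 and Day 28, and mode does not enter any model in Section 9.2. All three aims use this V_T. An imbalance in mode would be confounded with group in Aim 1 and with abstinence in Aim 3.

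**Working it through.** The plan gives no numerical figure on this point to reproduce. The check is of the estimator.

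**1. Algebra.** One-tissue model: dCt/dt = K1·Cp − k2·Ct, with V_T = K1/k2.
- Steady levels: dCt/dt = 0, so Ct/Cp = K1/k2 = V_T.
- Terminal phase after a bolus, with Cp falling at rate beta < k2: Ct/Cp tends to K1/(k2 − beta) = V_T × k2/(k2 − beta), which exceeds V_T.

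So equilibrium after a bolus can at most mean a constant ratio, at a value above V_T.

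**2. Terminal limit under assumed kinetics.** The documents give no rate constants. Assume k2 of 0.02-0.05/min and a late plasma half-life of 90-240 min, with beta = ln 2/half-life.
- k2 0.02, half-life 90 min (beta 0.0077): 0.02/(0.02 − 0.0077) = 1.63, or +63%.
- k2 0.05, half-life 240 min (beta 0.0029): 0.05/(0.05 − 0.0029) = 1.06, or +6%.

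These are limits. Tissue need not have reached them by 90-120 minutes.

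**3. Bias in the actual window.** Bi-exponential plasma curve, fast rate 0.15/min, same k2 and half-life ranges; mean tissue over mean plasma at 90-120 min, relative to V_T. The share of initial plasma in the fast phase is also unknown and is varied:

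| Fast-phase share | Bias, lowest to highest |
|---|---|
| 50% | about 0% to 24% |
| 80% | 7% to 35% |
| 90% | 9% to 56% |
| 95% | 13% to 99% |

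The plasma-curve shape drives the size. At k2 0.02 and half-life 90 min, the bias is 22% with a 50% share and 99% with a 95% share.

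**4. Infusion is not error-free.** With a different assumed curve (tri-exponential, terminal half-life 60-180 min, k2 0.02-0.05/min, bolus worth 100-300 min of infusion), bolus plus infusion gives 0.90 to 1.30 times V_T. Among the simulated cases where plasma changed by no more than about 3% per hour over 90-120 min, the range is 0.96 to 1.07. Plasma constancy is therefore a useful check whichever mode is used.

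**5. Scale.** Section 9.2 powers Aim 1 at d = 0.82. If the between-subject CV of V_T is 10% to 25% (assumption), that is 0.82 × 10% = 8.2% to 0.82 × 25% = 20.5% of the mean.

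**6. If modes were mixed (illustration only).** A share p of bolus scans in one group, each biased by b, shifts that group's mean by p × b. With b = 30%, p = 1/3 gives 10% and p = 1/2 gives 15%. Simulating Aim 1 with no true difference, 30 per group, CV 20%, and no bolus scans in the other group, the two-sided 5% test rejects in about 36% and 67% of runs respectively.

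**The case against.** The strongest reply is that infusion is the working plan. Section 6.1.1 names only that mode, and the acquisition text in the synopsis speaks of subjects being infused and of steady levels. If every scan follows Section 6.1.1, the bolus problem does not arise. This stands as a limit on the consequence. It does not resolve the contradiction, because the synopsis expressly provides for the bolus and nothing says which text governs.

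Four stronger readings are tempting and are not supported:

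- **That the study will show a false group or abstinence difference.** No section schedules bolus scans, assigns them to a group or visit, or expects mixing. The risk is conditional.
- **That a bolus scan always overstates V_T by a large, known amount.** The direction is certain only in the terminal phase. At k2 0.02, half-life 240 min and a 50% fast share, the 90-120 minute bias is about zero. Any single percentage rests on kinetics the documents do not give.
- **That a bolus scan could not be rescued by kinetic modelling.** This assumes the late 30-minute acquisition would apply to it. The documents do not describe acquisition for a bolus scan; the supported statement is that no valid acquisition and estimator are specified.
- **That the 15-20% differences cited in Section 9.2 are the benchmark.** Those are CB1 differences, not mGluR5.

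The arterial-line allowance is a small matter. It needs co-enrolment, a line already in place and failed intravenous access, and the swap is harmless at equilibrium. It can occur only in CUD subjects, so it merits a flag.

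**Conclusion.** The point holds. The synopsis and Section 6.1.1 contradict each other on tracer administration, and the single V_T method described is valid at equilibrium only. A bolus scan analysed as written would generally give a value that is not V_T and that varies with clearance. That follows from the algebra.

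The size does not. Under the assumed one-tissue model it runs from about 0% to about 100%, and the upper part of that range needs a 95% fast-phase share together with slow tissue washout. For comparison, the Aim 1 design difference is about 8% to 21% of the mean under the assumed CVs. Harm to the group or visit comparison further requires mixed modes, which the plan neither schedules nor excludes. Because the affected quantity is the primary outcome and the repair is cheap, it should be settled before further scans are acquired.

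**What to change.** 1. Reconcile the synopsis PET methods and Section 6.1.1 on how the tracer is given. Which mode to keep is for the sponsor to decide.
2. State that the mode is the same in both groups and at both visits, and record it for every scan.
3. For any mode retained, state the acquisition and a V_T estimator valid for that mode.
4. Use the 90-120 minute tissue-to-venous ratio only where the plasma samples already drawn in that window meet a numerical constancy threshold. Fix the threshold in advance and have it applied by someone unaware of group and visit. Section 6.3 marks blinding as not applicable, so without this the check would leave room for discretionary exclusions. Report how many scans fail, by group and visit.
5. As a minor addition, flag scans with arterial samples and repeat the Aim 1 and Aim 3 analyses without them.

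The cost is protocol wording and one check on blood data already collected. The downside is less operational flexibility and an occasional scan that cannot be used by the ratio method.

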#### C.2.c Electroencephalography (EEG) Methods:

General EEG Data Acquisition, Recording, and Preprocessing: EEG recording and preprocessing will be performed as described previously. Briefly, EEG data will be collected in an acoustically and electrically shielded booth, and recording will be done with the commercially available Active Two acquisition system (Biosemi, the Netherlands). A sampling rate of 1024 Hz will be utilized, with on-line low-pass filter of 256 Hz to prevent aliasing of high frequencies. A 64-channel electrode cap according to the extended 10-20 system will be used, along with additional electrodes to record the vertical and horizontal electro-oculogram. All electrodes will be referenced during recording to a common-mode signal (CMS) electrode between POz and PO3 and then subsequently re-referenced to the nose offline. EEG data will be first bandpass filtered from 0.1 — 100 Hz (24 dB/oct) and notch filtered at 60 Hz. Depending upon the particular stimulus parameters of each experiment (see below), the recorded EEG will be segmented into epochs consisting of the time period during stimulus presentation, along with a 100-300 ms baseline period. Any trial with a voltage greater than  $\pm 100 \,\mu\text{V}$  will be considered an artifact (i.e., movement, etc.), and will be excluded from the analysis. Ocular movement correction will be applied using Gratton's algorithm. 102 All EEG data preprocessing will be performed using the software package Analyzer 2.0 (Brain Products GmbH, Germany). Time-Frequency Analyses: Induced/Evoked Power and Intertrial Coherence (Phase Locking Factor): Timefrequency analyses will be the primary dependent measures in the proposed studies, along

with event-related potentials (ERPs), and will be performed as described previously. Baseline normalized evoked/Induced power and Interelectrode Coherence (ITC; also termed phase locking factor) will be determined using a wavelet-based time-frequency spectrogram via Analyzer 2.0. EEG Source Analysis: Standardized Low Resolution Brain Electromagnetic Tomography (sLORETA): Based on the scalp-recorded electric potential distribution, standardized low resolution brain electromagnetic tomography (sLORETA) will be used to compute the cortical three-dimensional distribution of current density. This will allow us to examine mGluR5 availability in ROIs in relation to EEG sources. The particular form of standardization used in sLORETA endows the tomography with the property of exact localization to test point sources, yielding images of standardized current density with exact localization, albeit with low spatial resolution (i.e. neighboring neuronal sources will be highly correlated). 104,105 sLORETA is the method of choice since it has no localization bias even in the presence of measurement and biological noise. 104 Furthermore, sLORETA has been validated in several simultaneous EEG/fMRI studies,  and in an EEG localization study for epilepsy.  In the current implementation of sLORETA, computations will be made both in a realistic head model,  using the MNI152 template,  and using each subject's structural MRI, with the three-dimensional solution space restricted to cortical gray matter, as determined by the probabilistic Talairach atlas. The intracerebral volume is partitioned in 6239 voxels at 5 mm spatial resolution. C.2.d. EEG Paradigms: RAVLT Task: A modified computer version of the Rey Auditory Verbal Learning Test (RAVLT) similar to Babiloni et al. (2009) will be utilized. The RAVLT will be administered while EEG data are collected in three separate conditions. In the passive listening condition, subjects will passively listen to a list of 15 words (presented one at a time) six times in a row. In the memory encoding condition, subjects will be administered a list of 15 words played one at a time, five times, and will be told to try and remember the list and to repeat as many words as possible after each list. A sixth distractor list will also be administered after the primary list as in the standard RAVLT. The inclusion of separate passive listening (which is not part of the standard RAVLT) and memory/encoding conditions will be included in order to compare neural signatures for both basic linguistic processing and processes related to memory encoding. Twenty minutes after the end of the encoding phase, subjects will be asked to repeat as many words as they can from the original list of words (the free recall phase). EEG will not be collected during the free recall phase. Following free recall, subjects will engage in a computerized recognition condition of the RAVLT. Subjects will hear words from the (1) original memorized list, (2) the distractor list, and (3) novel words not heard that day. Subjects will respond with a three-choice button box to indicate from which list each word originated. Words in the recognition condition will be presented every 4 seconds. This EEG version of the RAVLT allows separate examinations of neural oscillations during passive listening, memory encoding, and recognition. In addition, the words will be post-hoc sorted based on correct performance to examine activity during encoding for words that were accurately recalled (the "subsequent memory effect"). LTP Task: We induce and measure LTP using EEG with repetitive sensory stimulation. 100 This paradigm has been shown to have the properties of LTP including (1) frequency dependency, (2) temporal stability, (3) input specificity, and (4) de-potentiation by low frequency stimulation.  Tone pips (tone frequency 1000 Hz, presented for 50 msec) will be used in all stages of the task (i.e., for baseline, tetanus, and post-tetanic recording). During the baseline recording, 120 tone pips will be

presented with a variable inter-stimulus interval between 1800 — 2600 msec. After the baseline recording, LTP will be induced using auditory tetanus. The tetanus will consist of two minutes of the tone pips presented at 13 Hz. Subsequently, the test phase will commence, which will consist of another presentation of 120 tone pips as in the baseline period. The primary outcome measure will be N100-P200 amplitude after the auditory tetanus versus before the tetanus. The N100-P200 complex will be determined via automated algorithms and verified manually as described previously. 112

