#### Schema

#### Schedule of Activities (SoA)

OUTCOMES	SOURCE/MEASURE	нс	CUD (baseline) Day 0	CUD (abstinence) Day 28
Neural Recepto	ors			
mGluR5 Availability	PET ROI's $V_T$ : OFC, anterior cingulate, vmPFC, dlPFC, hippocampus, amygdala	X	X	X
Cannabis Use Disorder — Clinically Relevant Functional Measurements				
CUD Severity	DSM-5		X	
Cannabis Use Patterns	Timeline Follow Back		X	X
Cannabis Withdrawal Severity	Cannabis Withdrawal Scale		X	X
Cannabis Craving	7-point Scale		X	X
Cannabis- Related Problems	Marijuana Problems Scale		X	
Impulsivity	BIS/BAS	X	X	

Reward Processing	Probabilistic Reward Task	X	X	X
Mood	HAM-D, MADRS, Visual Analog Scale for Mood States	X	X	X
Sleep	Pittsburgh Sleep Quality Index	X	X	X
Cannabis Biomarkers				
Cannabis Use Status	Urinary THC-COOH*	X	X	X
Neural Function				
Verbal Memory	EEG: Theta band power/coherence	X	X	X
Synaptic Plasticity / LTP	EEG: N100-P200 amplitude increase after auditory tetanus	X	X	X
Neurocognitive Function	CogState Cognitive Battery	X	X	X

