Aim 3: Within CUD subjects, to determine changes in mGluR5 availability, EEG, and neurocognition following cannabis abstinence. Hypothesis 3: Following cannabis abstinence: (a) mGluR5 will decrease; (b) theta power/LTP will be increased; (c) memory will improve. Power Calculations for Hypothesis 3: Using the same standards applied for Aims 1 and 2, we considered our preliminary data and conducted a literature review to determine the magnitude of effect sizes we might reasonably expect to observe with respect to change in mGluR5, EEG, and cognition as a function of abstinence from cannabis. Values necessary to calculate associated effect sizes were not provided in the reviewed literature. For example, Hirvonen and colleagues (2012) observed a significant increase in CB1 receptor availability in cannabis users after abstinence in both the PFC and amygdala. While percent change (pre-post abstinence) could be roughly estimated from the figure provided, exact values are not available, preventing effect size estimation. We do not have preliminary data examining participants pre- and postcannabis abstinence. However, we believe that comparison of available PET data showing in vivo mGluR5 availability in current cannabis users compared with former users may be indicative of the magnitude of change we can expect to see following abstinence. Comparison of mGluR5 availability in current and former cannabis users in our preliminary sample (n= 5 per group) showed a large effect (d = -1.2). We will evaluate Hypothesis 3 using repeated measures ANOVA. Using a moderate effect size estimate of d = 0.58 at  $\alpha = 0.05$  (highly conservative relative to the noted relevant finding in our preliminary data), a priori power analysis suggested we will require n = 30 to achieve 80.13% power for the planned analysis. Data analysis for Hypothesis 3: To test Hypotheses 3, we will conduct 3 repeated measures ANOVAs to examine changes pre- and post-cannabis abstinence in n = 30 CUD subjects. Specifically, models will evaluate: (1) changes in mGluR5 availability; (2) changes in  $\theta$ -band power and coherence; (3) changes in cognition pre-post abstinence from cannabis in the CUD group. Variables that differ significantly between groups, including age and sex, will be considered for entry into the models. A statistically significant result indicative of lower mGluR5 availability following abstinence (model 1) or higher  $\theta$ - band power and coherence (model 2) and improved cognition (model 3) will be considered supportive of Hypothesis 3.

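### Theta intertrial coherence is a raw phase-locking factor that rises as trials fall; no trial-count correction is stated, and any recall-sorted comparison is the most exposed

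*Combined protocol and SAP*

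**What the plan says.** In the Synopsis, C.2.c (EEG Methods), the time-frequency heading reads "Induced/Evoked Power and Intertrial Coherence (Phase Locking Factor". The text under it reads "Baseline normalized evoked/Induced power and Interelectrode Coherence (ITC; also termed phase locking factor) will be determined". Time-frequency "analyses will be the primary dependent measures in the proposed studies, along" with event-related potentials. The computation is otherwise referred to earlier publications.

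Two rules make the number of trials vary. A trial above ±100 µV "will be considered an artifact (i.e., movement, etc.), and will be excluded from the analysis". In the verbal learning task (C.2.d), "the words will be post-hoc sorted based on correct performance to examine activity during encoding for words that were accurately recalled".

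The Schedule of Activities and Section 8.1 list "EEG: Theta band power/coherence" for controls and for CUD subjects at Day 0 and Day 28. Among the Aim 3 repeated measures models in Section 9.2, the second is on change in theta-band "power and coherence; (3) changes in cognition pre-post abstinence from cannabis in the CUD group" (the quotation runs on into the third model). Higher coherence after abstinence counts in favour of Hypothesis 3.

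I found no minimum number of retained trials, no rule for matching trial counts, and no bias-corrected estimator. The text also leaves open whether 'baseline normalized' applies to coherence or only to power.

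**The concern.** Intertrial coherence is the consistency of phase over trials at one site. Interelectrode coherence is coupling between sites. The text should name one of them.

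The statistical issue is the estimator. The PLF is the length of the average of N unit phase vectors. Even with random phases that length is above zero, and it grows as N shrinks. Two conditions with the same true phase locking but different trial counts therefore have different expected PLFs.

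In a recall-sorted analysis the trial count is the subject's own recall score, so a recalled v not-recalled difference in coherence could reflect nothing but how many words were remembered. The same would hold for a Day 0 v Day 28 comparison limited to recalled words if memory improves, as Hypothesis 3(c) predicts.

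**Working it through.** **Plan's own figure.** None is given for coherence or for trial counts, so there is nothing to reproduce.

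**Inputs from the documents.** Encoding presents 15 words × 5 = 75 trials before rejection. The CUD group has n = 30 and α = 0.05.

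**Inputs assumed.** No recall or rejection rates are given, so I take:
- recalled v not recalled: 45 v 30 (9 and 6 words × 5), 55 v 20 (11 and 4 words × 5) and, as a near-even split, 40 v 35 (8 and 7 words × 5);
- Day 0 v Day 28, all encoding trials, with unequal rejection: 75 v 60;
- Day 0 v Day 28, recalled words only: 45 v 60 (9 rising to 12 words × 5);
- true phase locking ρ of 0, 0.1, 0.2 or 0.3, the same in both conditions.

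**Formulas.** E[PLF²] = ρ² + (1 − ρ²)/N. At ρ = 0, E[PLF] ≈ √(π/(4N)) and Var(PLF) ≈ (1 − π/4)/N = 0.2146/N. The expected PLF with no phase locking is then 0.102 at 75 trials, 0.114 at 60, 0.120 at 55, 0.132 at 45, 0.162 at 30 and 0.198 at 20.

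**Hand check at ρ = 0, paired t-test, critical value 2.045 on 29 df.**
- 55 v 20: difference 0.1195 − 0.1982 = −0.0787. SD of the difference √(0.2146 × (1/55 + 1/20)) = 0.121. SE 0.121/√30 = 0.0221. Ratio 3.56, so the test rejects about 93% of the time.
- 45 v 30: difference 0.1321 − 0.1618 = −0.0297. SD 0.109, SE 0.0199, ratio 1.49, so about 30%.

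**Simulation.** Von Mises phases, 30 subjects, paired t-test, 4,000 replicates per cell. Entries are rejection rates under no true difference.

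| Trials | ρ = 0 | 0.1 | 0.2 | 0.3 |
|---|---|---|---|---|
| 45 v 30, raw | 31% | 19% | 10% | 7% |
| 55 v 20, raw | 95% | 77% | 35% | 16% |
| 40 v 35, raw | 8% | 7% | 6% | 5% |
| 75 v 60, raw | 13% | 8% | 6% | 5% |
| 45 v 60, raw | 17% | 11% | 7% | 5% |
| 55 v 20, baseline-subtracted | 5% | 6% | 15% | 27% |

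Repeat runs agree to within about three percentage points.

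**Direction.** For raw PLF at 55 v 20 the recalled class looks lower, by 0.079, 0.067, 0.046 and 0.029 as ρ goes from 0 to 0.3. If a baseline PLF with no phase locking is subtracted, the bias is nil at ρ = 0 and then reverses: +0.013, +0.033 and +0.051 at ρ = 0.1, 0.2 and 0.3. For recalled words at 45 v 60, raw PLF shows a false fall at Day 28, against Hypothesis 3. With baseline subtraction it shows a false rise of about 0.01 at ρ = 0.2, and the rejection rate is only about 6%.

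**Corrected estimator.** Pairwise phase consistency is (N × PLF² − 1)/(N − 1). Its expectation is (Nρ² + 1 − ρ² − 1)/(N − 1) = ρ²(N − 1)/(N − 1) = ρ², whatever N is. In the same simulations its bias was at most 0.0004 and its rejection rate 4 to 6%. Raw PLF at equal counts (75 v 75) also held at about 5 to 6%.

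**The case against.** The case on the other side is substantial, and most of it stands.

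- **Naming.** A reader might infer that coherence is two different endpoints. The documents do not support that: the heading, the abbreviation ITC and the gloss 'phase locking factor' all point to the intertrial measure. This is an editorial correction.
- **No correction.** One might infer that the PLF will be used uncorrected. The method is deferred to cited papers that are not available here, so only the absence of a stated correction can be claimed.
- **Recall sorting.** The plan speaks of activity during encoding and does not name coherence. It specifies no recalled v not-recalled test, no hypothesis rests on one, and Section 9.2 does not analyse one. The largest error rates therefore belong to an analysis that the plan allows but does not define. Coherence is still a natural candidate, because time-frequency measures are the main EEG outcomes.
- **Day 0 v Day 28.** It is tempting to say that better memory biases the abstinence result. As written, the Aim 3 model is not limited to recalled words, and 75 encoding trials are presented at each visit whatever the subject remembers. Only a difference in artifact rejection between visits can shift it, and if retained counts are equal on average there is no bias.
- **Reach.** EEG is secondary and optional, and Hypotheses 2 and 3 name theta power and LTP, not coherence.

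What remains is that a raw PLF depends on trial count, that recall sorting makes counts unequal whenever recall is not near half, and that no safeguard is stated.

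**Conclusion.** The point holds as a low-cost improvement to a secondary, optional measure. It does not show that the abstinence comparison is invalid.

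Any raw-PLF comparison by recall class would be unreliable when the split is uneven: about 7 to 31% false positives at 45 v 30 and 16 to 95% at 55 v 20, against 5 to 8% at 40 v 35. Baseline subtraction reverses the sign and reduces the error (about 5 to 27% at 55 v 20) without removing it, so even the direction depends on a definition the plan does not give. The Day 0 v Day 28 model over all encoding trials is exposed only to unequal rejection, and slightly (about 5 to 13% at 75 v 60). Limited to recalled words it would be about 5 to 17% at 45 v 60.

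The trial counts and true locking values are assumptions. The simulation uses one coherence value per subject with sampling noise only, and EEG on all 30 CUD subjects. Averaging over electrodes or a time window would raise the error for the same bias. Real between-subject variation in change, or fewer subjects with EEG, would lower it. V_T, induced theta power and the N100-P200 amplitude are not touched by this argument.

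**What to change.** 1. In C.2.c, replace 'Interelectrode' with intertrial and give the formula.
2. Compute intertrial coherence as pairwise phase consistency, (N × PLF² − 1)/(N − 1), keeping negative values. Alternatively, randomly subsample to the same number of trials within each subject across visits and recall classes.
3. State whether coherence is baseline-normalised and, if so, how.
4. Report retained trial counts by visit and recall class.

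The cost is a few lines of analysis script, with no new data and no participant burden. Subsampling discards some trials; pairwise phase consistency discards none, but it estimates ρ² and so is on a different scale from published PLF values. The choice should be fixed before the EEG data are analysed, because the raw and baseline-subtracted versions are biased in opposite directions.
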